6.6.3.1 Permitted Concomitant Therapies

The following concomitant medication and therapies are permitted during the trial:

1. SARS-CoV-2 vaccine is generally permitted, including mRNA-based, protein-based, or nonreplicating viral vector-based vaccines. Consider choosing an appropriate type of SARS-CoV-2 vaccine and consult with an infectious disease expert if desired. SARS-CoV-2 vaccine should not be administered during the screening period and DLT observation period.

Confidential Page 72 of 162

Document Number: TMF-380962

Version: 3.0

For other immunizations, physicians should review the subject's vaccination status and subjects should, if possible, be brought up to date with all immunizations in agreement with current immunization guidelines prior to initiating treatment.

Genmab

- 2. Hematopoietic growth factors such as erythropoietin, granulocyte colony-stimulating factor (G-CSF) (filgrastim, pegfilgrastim), granulocyte/macrophage colony-stimulating factor (sargramostim), or thrombopoietin (oprelvekin, eltrombopag) are permitted if clinically indicated. In the case of ≥ grade 3 neutropenia, use of growth factors is mandated in dose escalation and at the investigator's discretion in expansion.
- 3. Red blood cell and platelet transfusions, if clinically indicated.
- 4. Multivitamins, vitamin D, calcium, and supplements for prevention of weight loss.
- 5. Prescribed medicinal cannabinoids as palliative therapy.
- 6. Medications to prevent or treat CRS and ICANS are permitted. Please refer to Section 6.7.2 for AE management guidelines and mitigation plans.
- 7. It is recommended that high-risk subjects (ie, those with a high tumor burden) should be treated prophylactically in accordance with local standards (eg, rehydration, diuretics, allopurinol 300 mg daily, and medication to increase urate excretion). All subjects should be monitored for symptoms of TLS (see Section 10.15). Management of TLS, including dehydration and abnormal laboratory test results such as hyperkalemia, hyperuricemia, and hypocalcemia, is highly recommended.
- 8. Anti-infection prophylaxis for bacterial, viral, fungal, or pneumocystis infections is allowed and should be given per institutional practice.
- 9. Intravenous immunoglobulins are allowed to manage hypogammaglobulinemia at the investigator's discretion per institutional practice. Note, immunoglobulins administered at doses on the order of 1 g/kg body weight have the potential to alter the clearance of other antibodies. Investigators should therefore be aware that the efficacy of antibody-based agents, including GEN3017, may be decreased when administering immunoglobulins at these doses, eg, for the treatment of immune thrombocytopenia, or other immune, inflammatory, or paraneoplastic conditions.
- 10. Dexamethasone and other steroids may induce gastritis. Medications to prevent gastritis are permitted per institutional guidelines, for example proton pump inhibitors (omeprazole or equivalent) or sucralfate, or H2 blockers (ranitidine or equivalent).
- 11. Subjects who use oral contraceptives, hormone-replacement therapy, or other maintenance therapy should continue their use.

6.6.3.2 Prohibited Concomitant Therapy

The sponsor must be notified in advance (or as soon as possible thereafter) of any instances in which prohibited therapies are administered.

The following concomitant therapies are prohibited from C1D1 until 30 days after last dose of GEN3017 unless otherwise specified:

Confidential Page 73 of 162

Version: 3.0

1. Any anticancer therapy intended for the treatment of lymphomas, eg, cytotoxic chemotherapy, immunotherapy, radiotherapy or experimental therapy.

Note: Radiation therapy is prohibited during the first treatment cycle. After the first cycle, radiation is permitted for palliative use only if documented radiographic disease progression is ruled out first.

- 2. Corticosteroid that exceeds a total daily dose of 25 mg of prednisolone or equivalent administered for more than 14 days unless for the management of AEs (excluding corticosteroids given as GEN3017 pre-infusion medication as prophylaxis as described in Section 6.1.2).
- 3. Live vaccines received within 30 days of the first dose of GEN3017, at any time during GEN3017 treatment, and for 3 months following the last dose of GEN3017.

Note: Seasonal influenza vaccines are generally killed virus vaccines and are permitted; however, intranasal influenza vaccines are live attenuated and are not allowed.

- 4. In the dose escalation part, administration of SARS-CoV-2 vaccine during the screening period and DLT period is not permitted.
- 5. Participation in any other investigational or interventional studies is not permitted.

Subjects who require the use of any of these agents will be discontinued from GEN3017 treatment. The sponsor must be notified. Subjects who are discontinued from GEN3017 treatment will be followed for safety outcomes for 60 days following the last dose of GEN3017 or until the subject receives a new anticancer therapy, whichever occurs first.

The above lists of medications are not necessarily all-inclusive. The investigator should contact the sponsor's MM if questions arise regarding medications not listed above.

6.7 Dose Modification and Stopping Rules

6.7.1 Dose-Limiting Toxicity (Dose Escalation of GEN3017)

Treatment delays during the first CCI of the start of the DLT window are allowed if they are less than 1 cycle in length; under these circumstances, the DLT window can be extended up to CCI.

All DLTs are required to be reported to the sponsor within 24 hours of occurrence.

Confidential Page 74 of 162

Document Number: TMF-380962

Version: 3.0

All AEs including DLTs will be graded for severity according to the National Cancer Institute (NCI)-CTCAE, v5.0 unless otherwise specified. CRS and ICANS will be evaluated according to the ASTCT criteria (Lee et al., 2019). Clinical tumor lysis syndrome (CTLS) will be evaluated according to the Cairo-Bishop classification ((Coiffier et al., 2008); Section 10.15).

Genmab

The occurrence of any of the toxicities outlined in this section will be considered as a DLT except those that are clearly due to the underlying disease or extraneous cause:

- All grade 5 toxicities
- Hematological toxicities listed below:
 - o Grade 4 neutropenia (ie, absolute neutrophil count $<0.5\times10^9$ cells/L [$<500/\mu$ L]) lasting >7 days not attributable to underlying disease
 - o Grade 3 and grade 4 febrile neutropenia (neutrophil count <1.0×10⁹ cells/L with a single temperature of >38.3 °C [100.9 °F] or with a sustained temperature of ≥38 °C [≥100.4 °F] for more than 1 hour) lasting >2 days
 - Grade 4 thrombocytopenia (platelet count ≤25.0×10⁹ platelets/L [<25,000/μL]) for >7 consecutive days not attributable to underlying disease, or ≥ grade 3 thrombocytopenia (<50.0×10⁹ platelets/L) of any duration with clinically significant bleeding or ≥ grade 3 thrombocytopenia requiring a platelet transfusion
 - Grade 4 anemia
- Non-hematological toxicities listed below:
 - o Grade 4 CRS according to ASTCT criteria (Lee et al., 2019)
 - o Grade 3 CRS according to ASTCT criteria (Lee et al., 2019) which has not resolved to ≤ grade 2 within 48 hours following adequate intervention
 - o Grade 4 ICANS according to ASTCT criteria (Lee et al., 2019)
 - o Grade 3 ICANS according to ASTCT criteria (Lee et al., 2019) which has not resolved to ≤ grade 2 within 48 hours following adequate intervention
 - o TLS grade 3 that has not resolved within 5 days
 - o TLS grade 4
 - Any ≥ grade 3 (severe or life-threatening) non-hematological toxicities, excluding the following:
 - Laboratory values out of normal range that do not have any clinical consequence, are clinically transient in nature, and that resolve within 7 days (including electrolyte abnormalities that respond to medical intervention)
 - Grade 3 aspartate transaminase and/or grade 3 alanine transaminase returning to grade 1 or baseline in ≤10 days

Confidential Page 75 of 162

Document Number: TMF-380962

Version: 3.0

• Grade 3 nausea that responds to optimal antiemetic treatment in <3 days

- Grade 3 vomiting that responds to optimal antiemetic treatment in ≤ 3 days
- Grade 3 diarrhea that responds to optimal antidiarrheal treatment in \leq 3 days
- Grade 3 fatigue/asthenia when fatigue/asthenia was present at baseline or that lasts for <14 days after the last dose of GEN3017

Genmab

• Grade 3 amylase or lipase that is not associated with symptoms, or clinical manifestations, or radiological imaging of pancreatitis

Note: AEs of specified grades, regardless of relationship to GEN3017, should be considered relevant for dose escalation decisions, unless the event can clearly be determined to be unrelated to the drug. All of the AEs of specified grades should be classified as DLTs except those that are clearly and incontrovertibly due to the underlying disease or extraneous causes.

Frequent laboratory monitoring of complete blood count, including differential, should be initiated to document start and resolution of hematological AEs. All GEN3017-related AEs will be monitored and included in the evaluation of the toxicity profile of GEN3017 unless the event is clearly determined to be unrelated to GEN3017. AEs clearly not related to GEN3017 such as disease progression, environmental factors, unrelated trauma, etc, should not be considered as a toxicity event.

6.7.2 Dose Modification Guidance and Stopping Criteria

Dose modification such as increase or decrease of GEN3017 is not permitted for this trial. Dose delay of GEN3017 is permitted for this trial, as described below.

6.7.2.1 Dose Escalation Part (GEN3017 Monotherapy)

- If a subject experiences a DLT, GEN3017 treatment will need to be interrupted and further doses withheld while managing the DLT. The investigator is required to notify the sponsor's MM promptly and conduct a full assessment of the event and benefit-risk for the subject. The subject may continue treatment with GEN3017, if the toxicity recovers to ≤ grade 2 or baseline within 4 weeks from occurrence of the DLT. Continuous treatment with GEN3017 must be approved by the sponsor's MM. GEN3017 treatment will be permanently discontinued 1) in the event the DLT is not resolved to ≤ grade 2 or baseline within 4 weeks or 2) in the event a subject experiences a second episode of a DLT with GEN3017. Following a DLT of grade 4 non-hematologic toxicity, GEN3017 treatment should be immediately interrupted, and proper management of the AE should be initiated promptly. Resumption of GEN3017 may be considered under the following conditions after discussion with the MM: 1) grade 4 AE has improved to grade 2 or better; or 2) subject has shown clinical benefit from the GEN3017 treatment.
- If a subject experiences toxicity that would have qualified as a DLT but the event occurs after the DLT evaluation period, the subject's benefit-risk must be thoroughly assessed by the investigator. Continuous treatment with GEN3017 must be approved by the sponsor's MM.

Confidential Page 76 of 162

Version: 3.0

- For the subject who receives treatment beyond the DLT evaluation period, all corresponding
 AEs that would have met the DLT criteria will be considered for the purpose of determining
 the RP2D and/or MTD (if reached). For the declaration of the RP2D from the dose escalation
 for further development of GEN3017 in expansion, the totality of the data including safety,
 tolerability, immunogenicity, PK, pharmacodynamics, and preliminary efficacy will be
 evaluated.
- During dose escalation, a planned dose of GEN3017 can be postponed for up to 4 weeks due to an AE whether it is considered drug-related or not.
- In case of dose delay of more than 4 weeks from the last trial drug administration due to toxicity (not a DLT), continuous GEN3017 treatment may be considered if the subject is clearly benefiting from GEN3017 treatment (eg, imaging indicating clinical activity of GEN3017). Resuming GEN3017 must be approved by the sponsor's MM.
- During the trial, the GEN3017 dose can be held for the following laboratory results:
 - a. If platelet count is $<50 \times 10^9/L$, hold dose until platelet count is $\ge 50 \times 10^9/L$.
 - b. If febrile neutropenia is $<0.5 \times 10^9$ /L, hold dose until neutrophil count is $\ge 0.5 \times 10^9$ /L.
 - c. If hemoglobin is <8 g/dL (<80 g/L or <4.9 mmol/L), hold dose until hemoglobin is ≥8 g/dL (≥80 g/L or ≥4.9 mmol/L).

Note: If the investigator deems any of the above cytopenia as bone marrow involvement due to the disease, continuation of GEN3017 treatment can be discussed with the sponsor's MM. Transfusion with blood products and/or administration with G-CSF is permitted if clinically indicated.

If a dose delay occurs, then PK and biomarker assessments should be performed on or relative to the actual day of trial drug administration, not on the original scheduled administration day.

Refer to Table 6-4 for dose modification guidelines for specific AEs (including guidance for permanent discontinuation of treatment).

Table 6-4 Dose Modification Guidelines for Specific Adverse Events

	Adverse Event(s)	Toxicity Grade or Condition (CTCAE v5.0 Except ASTCT for CRS/ICANS and Cairo- Bishop for TLS/CTLS)	Adverse Event Management	
Immune system disorder		Grade 1 and grade 2	Withhold GEN3017 until resolution of CRS event. Provide supportive therapy and manage per current practice guidelines.	

Confidential Page 77 of 162

Version: 3.0

	Adverse Event(s)	Toxicity Grade or Condition (CTCAE v5.0 Except ASTCT for CRS/ICANS and Cairo- Bishop for TLS/CTLS)	Adverse Event Management
			If grade 2 CRS occurs with CC or beyond, administer CRS prophylaxis with the next dose until an GEN3017 dose is given without subsequent CRS (of any grade).
		Grade 3	Withhold GEN3017 until resolution of CRS event.
	CRS (see Section 10.12 and Section 10.13. If CRS is refractory to management, consider other causes		Ensure CRS symptoms are resolved for at least 72 hours prior to the next dose of GEN3017.
			If grade 3 CRS occurs or beyond, administer CRS prophylaxis with the next dose until a GEN3017 dose is given without subsequent CRS (of any grade).
	including		Hospitalize for the next dose of GEN3017.
	macrophage activation syndrome		Recurrent grade 3 CRS:
	and hemophagocytic		Permanently discontinue GEN3017.
	lymphohistiocytosis)		Manage CRS per current practice guidelines (Section 10.13) and provide supportive therapy, which may include intensive care.
		Cytokine blockade-	Permanently discontinue GEN3017.
		refractory ^a grade 3 for >72 hours or grade 4	Manage CRS per current practice guidelines (Section 10.13) and provide supportive therapy, which may include intensive care.
	ICANS (see Section 10.14)	Grade 1 and grade 2	Withhold GEN3017 until resolution of ICANS event to ≤ grade 1 for at least 72 hours.
			Provide supportive therapy and manage per current practice guidelines.
		Grade 3	Withhold GEN3017 until resolution of ICANS event to ≤ grade 1 for at least 72 hours.
			Provide supportive therapy, which may include intensive care, consider neurology evaluation, and manage per current practice guidelines.
			Recurrent grade 3 ICANS: Permanently discontinue GEN3017.
		Grade 4	Permanently discontinue GEN3017.
			Provide supportive therapy, which may include intensive care, consider neurology evaluation, and manage per current practice guidelines.
Hematological (see Section 6.7.2.1 for details) ^b	Platelet count decreased/	≥ Grade 3	Withhold GEN3017 until platelet count is ≥50 × 10 ⁹ /L.
	thrombocytopenia		Platelet infusions may be administered per institutional standards.
	Neutropenia and febrile neutropenia	≥ Grade 3	Withhold GEN3017 until neutrophil count is $\geq 0.5 \times 10^9 / L$.
			Use of growth factors is mandated.
	Anemia	≥ Grade 3	Withhold GEN3017 until hemoglobin is ≥8 g/dL (≥80 g/L or ≥4.9 mmol/L).
			Red blood cell infusions should be administered per institutional standards.

Confidential Page 78 of 162

Document Number: TMF-380962

Version: 3.0

	Adverse Event(s)	Toxicity Grade or Condition (CTCAE v5.0 Except ASTCT for CRS/ICANS and Cairo- Bishop for TLS/CTLS)	Adverse Event Management	
	TLS/CTLS	Any grade	Withhold GEN3017 until resolution of TLS/CTLS event.	
	Tumor flare reaction	Grade 3 and 4	Withhold GEN3017 until improvement to ≤ grade 1. Monitor for signs and symptoms of compression or obstruction due to mass effect secondary to tumor flare, and institute appropriate treatment (Section 10.15).	
	All other non- hematologic AEs	Grade 3a; first occurrence	Withhold GEN3017 until improvement to ≤ grade 2 or resolution to baseline.	
		Grade 3a; recurrent	Second episode of the same AE considered related to GEN3017:	
Other non-hematologic			Withhold GEN3017 until improvement to ≤ grade 2 or resolution to baseline.	
			Permanently discontinue GEN3017 if no improvement within 14 days unless otherwise agreed upon with the sponsor's medical monitor.	
		Grade 4a; first occurrence	Withhold GEN3017.	
			Initiate proper management of the AE.	
			Resume GEN3017 after discussion with the medical monitor and improvement to ≤ grade 2 or resolution to baseline, or subject has shown clinical benefit from GEN3017 treatment.	
		Grade 4ª; recurrent	Second episode of the same AE considered related to GEN3017: Permanently discontinue GEN3017 unless otherwise agreed upon with the sponsor's medical monitor.	

AE=adverse event; ALT=alanine transaminase; AST=aspartate transaminase; CRS=cytokine release syndrome; ICANS=immune effector cell-associated neurotoxicity syndrome; TLS=tumor lysis syndrome.

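### Section 6.7.2.1 lets clinical benefit replace recovery as the ground for resuming GEN3017 after a grade 4 non-hematologic DLT, against the recovery-within-4-weeks rule in the same bullet

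*Combined protocol and SAP*

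**What the plan says.** The first bullet of Section 6.7.2.1 sets a rule for every DLT. Dosing is interrupted, and the subject may continue "if the toxicity recovers to ≤ grade 2 or baseline within 4 weeks from occurrence of the DLT". The converse is mandatory: "GEN3017 treatment will be permanently discontinued 1) in the event the DLT is not resolved to ≤ grade 2 or baseline within 4 weeks". A second DLT also ends treatment. The bullet adds an approval step: "Continuous treatment with GEN3017 must be approved by the sponsor's MM".

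The bullet then turns to one subset, DLTs that are grade 4 non-hematologic toxicities. For these, resumption may be considered after discussion with the medical monitor (MM) if "1) grade 4 AE has improved to grade 2 or better; or 2) subject has shown clinical benefit from the GEN3017 treatment".

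Table 6-4 has a matching entry in the row "All other non- hematologic AEs". For a first grade 4 occurrence it allows resumption after MM discussion and "improvement to ≤ grade 2 or resolution to baseline, or subject has shown clinical benefit from GEN3017 treatment". It does not separate DLTs from other adverse events. For a first grade 3 occurrence, the same row requires improvement to grade 2 or lower, or return to baseline, and offers no benefit alternative.

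A later bullet in Section 6.7.2.1 has its own clinical-benefit exception for long delays. It opens "In case of dose delay of more than 4 weeks from the last trial drug administration due to toxicity (not a DLT", so DLTs are outside it.

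**The concern.** The two conditions after a grade 4 non-hematologic DLT are joined by an 'or', so clinical benefit alone satisfies the criterion. Such a DLT is also covered by the rule for all DLTs, which requires recovery and states no exception. No text says which criterion governs.

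At stake is rechallenge of a subject whose grade 4 toxicity has not recovered, in a first-in-human trial with no prior clinical experience (Section 2.1.2.2). Section 6.7.2 does not permit dose reduction, so the subject would receive the dose that caused the event. The investigator and the MM could each apply a different criterion to the same event and each cite the protocol.

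This is a matter of subject safety and clear dosing rules. The DLT is counted in the mBOIN design whether or not dosing resumes, so no dose decision, endpoint or analysis changes.

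**Working it through.** The main check is a comparison of rules; arithmetic enters only for the timing.

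**1. Same subject, two rules.** Take a grade 4 non-hematologic DLT in the residual Table 6-4 category, in a subject judged to be benefiting.

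| State of the event | Rule for any DLT | Grade 4 sentence |
|---|---|---|
| Recovered to grade 2 or lower within 4 weeks | May continue with MM approval | Resumption may be considered (condition 1) |
| Still grade 3 or 4, before week 4 | Criterion for continuing not met | Resumption may be considered (condition 2) |
| Still grade 3 or 4, at week 4 | Permanent discontinuation, unless that is the subject's baseline grade | Resumption may be considered (condition 2; no time limit stated) |

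The rules agree in the first row and differ in the other two.

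**2. Order of severity.** Compare two benefiting subjects who both have a residual grade 3 toxicity above baseline. One had a grade 3 DLT that has not improved; the other had a grade 4 DLT that improved by one grade. Only the second has a route back to treatment. The grade 3 and grade 4 first-occurrence entries of Table 6-4 show the same inversion.

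**3. Which events are reached.** Four event types have their own rows in Table 6-4 and are not affected:
- grade 4 CRS: permanent discontinuation;
- grade 4 ICANS: permanent discontinuation;
- TLS/CTLS: "Withhold GEN3017 until resolution of TLS/CTLS event";
- tumor flare, grade 3 or 4: withhold until grade 1 or lower.

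Read as a whole, the protocol therefore does not authorise re-dosing after grade 4 CRS or ICANS. Footnote a of the table may also take asymptomatic isolated laboratory abnormalities out of the residual row. What remains is other grade 4 non-hematologic DLTs that have not recovered. For non-DLT events the table's 'or' contradicts nothing.

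**4. Could benefit be documented in time?** DLTs are assessed in cycle 1 (Section 4.1.1). The first scheduled on-treatment scan is at Week 6 ± 7 days, counted from the first dose (Section 8.2). The recovery limit is 4 × 7 = 28 days from DLT onset. If onset is d days after the first dose, the limit ends before a scan on day s when d + 28 < s, that is, when d < s − 28.

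| First scheduled scan | s (days) | s − 28 |
|---|---|---|
| Earliest | 42 − 7 = 35 | 7 |
| Nominal | 42 | 14 |
| Latest | 42 + 7 = 49 | 21 |

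For a DLT starting less than 7, 14 or 21 days after the first dose respectively, the 4-week limit expires before any scheduled response scan. Unscheduled scans are allowed when clinically indicated, so documenting benefit is difficult rather than impossible. Cycle length is redacted, so the share of DLTs affected cannot be calculated.

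**The case against.** The best defence is that the two rules differ in force. Discontinuation at 4 weeks is mandatory and resumption is only permitted, so the discretion can be read as operating inside the stop. The exclusion of DLTs from the long-delay exception supports that reading. The bullet also opens by requiring doses to be withheld while the DLT is being managed, and an unrecovered grade 4 event would ordinarily still be under management. The investigator must carry out a full benefit-risk assessment, and the MM must approve. Rechallenge therefore cannot follow from condition 2 alone.

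This narrows the gap but does not close it. If the 4-week stop caps everything, the last row of the first table is resolved, but the middle row is not: before week 4, condition 2 still allows resumption without recovery. The withholding sentence does not say when management ends. MM approval settles who decides, not which criterion applies.

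A second defence is that the alternative is deliberate, since it appears in both the text and the table and the subjects have exhausted, or are ineligible for, standard therapy. That is possible. But no text marks it as an exception to the rule for all DLTs, and a deliberate exception would be expected to say why grade 4 is treated more leniently than grade 3.

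A third point is that the timing in step 4 makes condition 2 hard to invoke on scan evidence, so it may seldom be used. That is fair, and it limits the practical weight of the point.

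**Conclusion.** The concern holds. Section 6.7.2.1 states two incompatible criteria for resuming GEN3017 after a grade 4 non-hematologic DLT, and Table 6-4 repeats the looser one. On the reading most favourable to the plan, with the 4-week stop overriding, same-dose rechallenge of an unrecovered grade 4 DLT can still be considered before week 4.

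The affected group is small: DLTs in dose escalation that are grade 4, non-hematologic, without their own Table 6-4 row and not recovered. No frequency is claimed, because the documents give no event rate. The conclusion assumes that events with their own row follow that row. The wording should be corrected, but the MM's involvement and the narrow reach limit the risk. Section 6.7.2.2 carries this guidance into expansion where appropriate, so the correction should come before then.

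**What to change.** In Section 6.7.2.1:
- Delete condition 2 as a stand-alone route. Do not change 'or' to 'and': that would bar recovered subjects who have no documented benefit.
- State instead: *Resumption after any DLT, including grade 4 non-hematologic, requires recovery to grade 2 or lower, or to baseline, within 4 weeks, and MM approval. Clinical benefit is only a factor in the benefit-risk discussion.*
- Add that non-hematologic events with a stricter row of their own in Table 6-4 follow that row, naming grade 4 CRS and grade 4 ICANS as permanent stops. This largely restates the section's existing pointer to the table, but it makes the sentence safe to read alone.

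In Table 6-4, residual non-hematologic row, grade 4, first occurrence: state that the clinical-benefit alternative does not apply to events that are DLTs.

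The cost is protocol wording in two places. Subjects who recover in time lose nothing. A few benefiting subjects with an unrecovered grade 4 DLT could not resume, which is what the rule for all DLTs already requires.
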